16.1. Study-Specific Design Considerations	
Revised text in this section (under subheading “Selection of subjects”) as follows (strikethrough text deleted; bold text added):
 
All subjects will be from Phase 3 studies ESKETINTRD3001, ESKETINTRD3002, ESKETINTRD3003, ESKETINTRD3004, and ESKETINTRD3005, and ESKETINTRD3006 (US Sites only).
 
For subjects who have participated in the ESKETINTRD3003, ESKETINTRD3004, and ESKETINTRD3005 studies and have responded to intranasal esketamine treatment, or did not the meet study criteria for response but per clinical judgment have benefitted, it is considered an ethical obligation to provide continued intranasal esketamine treatment if the benefit/risk profile is favorable for the subject at the time of completion of the previous study.
 
For subjects who have completed the induction phase of ESKETINTRD3005 or ESKETINTRD3006 (US Sites only) and are non-responders did not meet the study criteria for response, or for subjects who have completed the induction phase and 6-month 2-week follow up phase visit of the ESKETINTRD3001 or ESKETINTRD3002 study, as the double-blind treatment (intranasal esketamine or placebo) in these studies will be blinded, the second induction phase of this study provides the following:
 
 • Subjects who are non-responders to intranasal placebo and oral antidepressant in the prior study have the potential of receiving esketamine in this study, and • Subjects who are non-responders to intranasal esketamine in the prior study who decide to participate in this study may not benefit from additional treatment with intranasal esketamine. The benefit of additional treatment with esketamine remains unknown. In case of no perceived benefit of intranasal esketamine to the subject during this study, the subject and/or investigator may choose to discontinue study participation.

Applicable Section(s)	Description of Change(s)
	
Rationale: To allow more flexibility when clinically indicated, the sponsor is removing the requirement that a subject should rollover from the parent study within a specific period of time. There is now no maximum duration between completing the parent study and starting the 54135419TRD3008 study

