- Changes from baseline over time in clinical laboratory tests, including hematology, serum chemistry, and urinalysis
- Time to discharge readiness, using the Clinical Global Assessment of Discharge Readiness (CGADR)

Efficacy endpoints include changes from baseline over time for the following:

- Depressive symptoms, including response ($\geq 50\%$ improvement from baseline) and remission (MADRS total score ≤ 12 , PHQ-9 total score < 5); using the Montgomery Asberg Depression Rating scale (MADRS) and 9-item self-reported Patient Health Questionnaire (PHQ-9)
- Overall severity of illness, using the Clinical Global Impression Severity (CGI-S)

- Functioning and associated disability, using the Sheehan Disability Scale (SDS)
- Health related quality of life and health status, using the European Quality of Life (EuroQol) Group, 5-Dimension, 5-Level (EQ-5D-5L)
- Health related quality of life using the Quality of Life in Depression Scale (QLDS)

Exploratory endpoints include:

- Changes from baseline over time for:
 - Depression response and remission rates (as defined above) to a second induction phase in eligible subjects who had relapsed in study ESKETINTRD3003, assessed using the MADRS and PHQ-9
 - Subject treatment satisfaction
- Subject tradeoff preferences for key benefit and harm outcomes associated with TRD treatment, using a stated-choice preference survey

Hypothesis

There is no formal hypothesis for this study.

OVERVIEW OF STUDY DESIGN

This is a multicenter, open-label long term extension study to evaluate the safety, tolerability, and efficacy of esketamine nasal spray in subjects with TRD.

The table below describes the subjects who may be eligible to participate in this study based on the clinical judgment of the investigator and their point of entry into 54135419TRD3008:

Prior Study	Inclusion requirement	Point of entry for 54135419TRD3008
ESKETINTRD3001	Subject completed induction phase and the 2- week follow-up phase visit	Induction phase
	Subject completed the induction phase and was a responder and ESKETINTRD3003 is terminated.	Optimization/maintenance phase
ESKETINTRD3002	Subject completed induction phase and the 2- week follow-up phase visit	Induction phase
	Subject completed the induction phase and was a responder and ESKETINTRD3003 is terminated.	Optimization/maintenance phase
ESKETINTRD3003	Subject relapsed in maintenance phase	Induction phase

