3.2. Study Design Rationale

3.2.1. Study Population

The study population will include adult and elderly men and women who previously participated in studies *ESKETINTRD3001*, *ESKETINTRD3002*, *ESKETINTRD3003*, *ESKETINTRD3004*, or *ESKETINTRD3005*, or *ESKETINTRD3006* (US sites only).

Options for the treatment of TRD are limited. For subjects who have participated in studies *ESKETINTRD3003*, *ESKETINTRD3004*, *ESKETINTRD3005* or *ESKETINTRD3006* (US sites only) studies and have responded to esketamine nasal spray treatment, it is considered an ethical obligation to provide continued esketamine nasal spray treatment if the benefit/risk profile is favorable for the subject at the time of completion of the previous study. Subjects in the placebo-controlled, double blind *ESKETINTRD3005* and who are non-responders at the end of the induction phase are eligible to enter the open label induction phase of *ESKETINTRD3004*, therefore if enrollment in the *ESKETINTRD3004* is complete these subjects will be given the opportunity to enter this study, if clinically appropriate. For subjects who have completed the induction phase and 6-month follow up phase of the *ESKETINTRD3001* or *ESKETINTRD3002*

study, this study provides an opportunity for subjects to have an induction phase with open-label esketamine nasal spray.

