3.2.2. Study Phases

Induction Phase (4 week; if applicable)

The duration of the 4-week open-label phase was selected because this is the duration of the induction phase in the prior studies from which these subjects are entering. It is unknown whether a second, repeated induction phase may be efficacious in subjects who have relapsed following response to esketamine nasal spray treatment (ESKETINTRD3003), have not responded to intranasal treatment with esketamine or placebo (ESKETINTRD3001 and ESKETINTRD3002, ESKETINTRD3005 and ESKETINTRD3006 [US sites only]), or with sponsor's approval, subjects not meeting criteria for response from ESKETINTRD3003 and ESKETINTRD3004, therefore this study will implement the same duration of the subject's first induction phase.

Optimization/Maintenance Phase (Variable)

The duration of the optimization/maintenance phase is variable and based on the subject's individual efficacy and tolerability to esketamine nasal spray, or when esketamine is approved in the respective country and accessible through the local healthcare system funding or until end of December 2022, whichever is earlier.

Subjects entering this phase from the induction phase of this study (54135419TRD3008) will reduce the frequency of intranasal treatment sessions and subsequently individualize and stabilize the treatment session frequency to weekly, every other week, or every 4 weeks based on the severity of depression during this phase.

All other subjects will enter this phase at the same frequency of intranasal treatment sessions that they had in the prior study, and this phase will allow the frequency of intranasal treatment sessions to continue to be individualized to once weekly, once every other week, or once every 4 weeks based on the severity of depression in order to sustain antidepressant efficacy.

While there is not a separate follow up phase, to ensure subject safety, an End of Study visit will be planned to occur within 1 week of the last esketamine nasal spray treatment.

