The rationale for allowing reduction in the frequency of intranasal treatment sessions from twice weekly to weekly, once every other week, or once every 4 weeks, is to individualize the treatment session frequency (weekly, every other week, or every 4 weeks) for a given subject (based on level of depressive symptoms). Open label data from Panel A of a recently completed study (ESKETINTRD2003), indicates that even with a reduction in dosing frequency from twice weekly to weekly for 3 weeks and then a reduction to every other week for an additional 4 week, the majority of patients were able to maintain their treatment response. Additional data from the 8-week follow up phase of ESKETINTRD2003 indicates that most patients who were responders when entering the follow up phase were able to maintain their response for up to 8 weeks after cessation of intranasal dosing. Therefor the current study will provide an opportunity to evaluate the impact of dosing every 4 weeks, which has not been studied in the other Phase 3 protocols to date. Similarly, anecdotal reports from clinical practice with IV ketamine, suggests patient may be able to maintain the antidepressant benefits achieved with less frequent dosing.

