4.1. Inclusion Criteria

Each potential subject must satisfy all of the following criteria to be enrolled in the study.

1. Criterion modified per Amendment 1

1.1 Based on the prior study the subject is entering 54135419TRD3008 from:

a. *From ESKETINTRD3001 or ESKETINTRD3002 study:*

- i. Subject has completed the induction phase and the 2-week follow up phase visit; or
- ii. Subject completed the induction phase and was a responder and study ESKETINTRD3003 is terminated.

b. *From ESKETINTRD3003 study:*

- i. Subject relapsed during the maintenance phase; or
- ii. Subject was in the induction phase of the ESKETINTRD3003 study when the study was terminated and, after completion of the induction phase, was determined to be a responder; or
- iii. Subject was in the optimization or maintenance phases at the time the study was terminated; or
- iv. At Week 16 of Optimization, the subject was not eligible to proceed to the Maintenance phase and sponsor has approved subject's entry into 54135419TRD3008; or
- v. Subject was in the induction phase and after completion of induction phase was determined to not meet response criteria, and sponsor has approved subject's entry into 54135419TRD3008.

c. *From ESKETINTRD3004 study:*

- i. Subject completed ESKETINTRD3004 study optimization/maintenance phase; or
- ii. Subject was in the induction phase of the ESKETINTRD3004 study when the study was terminated and, after completion of the induction phase, was determined to be a responder; or
- iii. Subject was in the optimization/maintenance phase at the time the study was terminated; or
- iv. Subject was in the induction phase and did not meet criteria for response, and sponsor has approved subject's entry into 54135419TRD3008.

d. *From ESKETINTRD3005 study: Subject was in the induction phase of the ESKETINTRD3005 study at the time enrollment into the ESKETINTRD3004 study was closed and, after completion of the induction phase, was determined to be a responder or did not meet the criteria for response.*

- e. *From ESKETINTRD3006 study (US Study sites only):*
- i. Subject completed the induction phase and was a responder; or
 - ii. Subject completed the induction phase and did not meet the response criteria and sponsor has approved subject's entry into 54135419TRD3008.

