1.2. Trial Design

This is a multicenter, open-label long term extension study to evaluate the safety, tolerability, and efficacy of intranasal esketamine in subjects with TRD. The study population will include adult and elderly men and women who previously participated in studies ESKETINTRD3001, ESKETINTRD3002, ESKETINTRD3003, ESKETINTRD3004, ESKETINTRD3005, or ESKETINTRD3006 (US sites only) and will have met the inclusion/exclusion criteria for entry into those prior studies.

For subjects who participated in studies ESKETINTRD3003, ESKETINTRD3004, ESKETINTRD3005 or ESKETINTRD3006 (US sites only) and have responded to intranasal esketamine treatment, it is considered an ethical obligation to provide continued intranasal esketamine treatment if the benefit/risk profile was favorable for the subject at the time of completion of the previous study. Subjects in the placebo-controlled, double blind ESKETINTRD3005 and who are non-responders at the end of the induction phase were eligible to enter the open label induction phase of ESKETINTRD3004, therefore if enrollment in the ESKETINTRD3004 had completed these subjects were given the opportunity to enter this study, if clinically appropriate. For subjects who completed the induction phase and 6-month follow up phase of the ESKETINTRD3001 or ESKETINTRD3002 study, this study provided an opportunity for subjects to have an induction phase with open-label intranasal esketamine.

An Independent Data Monitoring Committee (IDMC) is commissioned for this study to review safety data periodically.

This study (54135419TRD3008) has 2 open label phases:

- A 4-week induction phase (if applicable)
- A variable duration optimization/maintenance phase

The duration that a subject may participate in the study is variable and is based on the subject's point of entry into the study and the timing of when the predefined criteria (below) for ending study participation occurs.

Study participation will be stopped:

- At the time intranasal esketamine is commercially available or a pre-approval access program is available to the subject in the subject's respective country; or
- The subject no longer benefits from further treatment (based on the investigator's clinical judgment), or withdraws consent; or
- The company terminates clinical development of intranasal esketamine for TRD.

Subjects will have a final study visit within 1 week of the last dose of intranasal esketamine.

A description of the study phases is provided below.

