5.2.1. Montgomery-Asberg Depression Rating Scale (MADRS)

5.2.1.1. Definition

The MADRS is a clinician-rated scale designed to measure depression severity and to detect changes due to antidepressant treatment⁵. The scale consists of 10 items, each of which is scored from 0 (item is not present or is normal) to 6 (severe or continuous presence of the symptoms), for a total possible score of 60. Higher scores represent a more severe condition. The MADRS evaluates apparent sadness, reported sadness, inner tension, sleep, appetite, concentration, lassitude, interest level, pessimistic thoughts, and suicidal thoughts. The test exhibits high inter-rater reliability.

If 2 or more items are missing, no imputation will be performed and the total score will be left missing. Otherwise, the total score will be calculated as sum of the non-missing items multiplied by the ratio of the maximum number of items (i.e., 10) to the number of non-missing items.

A subject is defined a responder at a given time point if the percent improvement in MADRS total score is $\geq 50\%$.

A subject is defined as a remitter at a given time point if the MADRS total score of ≤ 12 at that time point.

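### Entry to induction from 3001/3002 requires neither non-response nor a Day 1 severity level, and the SAP does not separate remission already present at entry from remission reached during induction

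*Protocol*

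**What the plan says.** **Entry.** The protocol synopsis table gives the induction requirement for 3001/3002 as: "Subject completed induction phase and the 2- week follow-up phase visit". Table 1, Section 9.1.2 and the induction list in SAP 1.2 give the same rule. Inclusion criterion 1.1 a.i in Section 4.1 reads: "Subject has completed the induction phase and the 2-week follow up phase visit; or". The other induction routes each carry a condition on clinical status: relapse (3003), not qualifying for maintenance at Week 16 (3003), or not meeting response criteria (3003, 3004, 3005, 3006). Sections 4.1 and 4.2 set no MADRS, PHQ-9 or CGI-S level for Day 1. The nearest gate is the investigator's benefit-risk judgment.

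**Descriptions that differ.** Section 3.2.2 groups the 3001/3002 entrants with people who "have not responded to intranasal treatment with esketamine or placebo". Section 3.2.1 speaks of subjects who "completed the induction phase and 6-month follow up phase of the" parent study, and SAP 1.2 does the same: "For subjects who completed the induction phase and 6-month follow up phase of the ESKETINTRD3001 or ESKETINTRD3002 study". The criteria say 2 weeks.

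**Endpoints.** SAP 5.2.1.1: "A subject is defined as a remitter at a given time point if the MADRS total score of ≤ 12 at that time point". SAP 5.2.3.1 uses PHQ-9 below 5 in the same way. Response on either scale is at least 50% improvement, with change taken from the baseline of the respective phase (SAP 2.2, 5.2.1.2, 5.2.3.2). The analysis set is everyone dosed in induction (SAP 2.4.2). The only subgroup is the 3003 relapsers (SAP 2.5).

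**The concern.** A remission rate for a treatment phase is normally read as the proportion who reached remission during that phase. That reading needs subjects to start outside remission. Here the 3001/3002 route does not ensure it.

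The gap has a practical source. The direct optimization/maintenance route for 3001/3002 responders opens only once 3003 is terminated (criterion 1.1 a.ii). Until then, induction was the only listed way in for a responder who had not joined 3003.

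At stake are the induction response and remission rates, which belong to the secondary efficacy objective. For the 3003 relapsers, the same two rates form a named exploratory objective. Entry status, rather than treatment, could push the two rates in opposite directions.

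**Working it through.** The plan gives no sample size, power or expected rate for these endpoints, so there is no figure to reproduce. The SAP uses the label Baseline (IND) without defining it. I read it as the study baseline for induction entrants, which is the last observation on or before the first induction dose.

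**Step 1: arithmetic from the definitions.** Let b be the Day 1 MADRS, with b at most 12, and y the later score. Remission needs y ≤ 12. Response needs y ≤ b/2.

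- b = 12, y = 12: remitter, improvement 0%, non-responder.
- To respond, 12 must fall to 6 or less, 8 to 4 or less, and 4 to 2 or less.
- A 4-point move from 8 to 4 is a response.
- On the PHQ-9, a Day 1 score of 4 must fall to 2 or less.

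**Step 2: how Day 1 remitters would be classified.** This is an illustrative simulation in which every input is assumed: 400,000 draws per scenario, b uniform on 1-12 or 6-12, SD of change 3, 5 or 7, scores rounded and floored at 0.

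| Mean change | Remitters at end | Responders at end |
|---|---|---|
| +2 | 58-80% | 3-24% |
| 0 | 69-90% | 9-34% |
| -2 | 78-96% | 24-44% |
| -4 | 85-99% | 47-61% |

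Non-responders are the majority in 21 of the 24 scenarios. The three exceptions all combine a further mean improvement of 4 points with b uniform on 1-12.

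**Step 3: effect on the reported rates.** Let f be the share in remission on Day 1.

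Remission = (1 - f) × r0 + f × r1; response = (1 - f) × s0 + f × s1.

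Assumed inputs: r0 = 30% and s0 = 50% among subjects not in remission on Day 1; r1 = 80-95% and s1 = 20-45% among those who are.

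- f = 10%: remission 0.9 × 30 + 0.1 × (80 to 95) = 35.0-36.5%; response 0.9 × 50 + 0.1 × (20 to 45) = 47.0-49.5%.
- f = 20%: remission 0.8 × 30 + 0.2 × (80 to 95) = 40-43%; response 0.8 × 50 + 0.2 × (20 to 45) = 44-49%.

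**Step 4: sensitivity.** With the widest simulated values (r1 from 58.2% to 98.9%, s1 from 2.5% to 61.2%):

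- f = 10%: remission 27 + 5.8 = 32.8% to 27 + 9.9 = 36.9%; response 45 + 0.25 = 45.3% to 45 + 6.1 = 51.1%.
- f = 20%: remission 24 + 11.6 = 35.6% to 24 + 19.8 = 43.8%; response 40 + 0.5 = 40.5% to 40 + 12.2 = 52.2%.

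The upward push on remission holds throughout. The downward push on response is usual but not guaranteed.

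**The case against.** **The affected group may be small.** Entry rests on the investigator's judgment. A 3001/3002 responder could join 3003, or enter optimization/maintenance directly once 3003 had ended. What remains is a responder who skipped 3003, was in remission, and was still judged suitable for induction. The documents give no count. This stands. A reader might infer that the reported rates do contain pre-existing remission, but the text supports only that they could.

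**Two passages are easy to over-read.** Section 3.2.4 says of ESKETINTRD2003 that "most patients who were responders when entering the follow up phase were able to maintain their response for up to 8 weeks" after dosing stopped. That concerns maintained response, not MADRS at or below 12, and it comes from another study. Section 16.1 mentions 3001/3002 responders to placebo plus oral antidepressant who did not join the next study, but names no point of entry. Neither passage shows subjects entering induction in remission.

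**The relapsers.** The Amendment 1 log states: "There is now no maximum duration between completing the parent study and starting the 54135419TRD3008 study", and footnote b of the current induction schedule agrees. Recovery before Day 1 is therefore possible for a 3003 relapser, but nothing in the documents shows that it happens.

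**Part of the information is already planned.** SAP Table 3 summarizes baseline MADRS, PHQ-9 and CGI-S, though for the All Enrolled set rather than by phase. The PHQ-9 none-minimal category (0-4) is exactly the remission range. If baseline is shown in the severity table, the Day 1 PHQ-9 count will be there. No planned table relates outcome to Day 1 remission status, however, so this does not meet the point.

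**No decision depends on these rates.** The primary objective is safety, there is no hypothesis, and progression to the next phase is by clinical judgment. That limits the weight of the point. It does not change what the rates count.

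**Conclusion.** The point holds as one of interpretation and reporting. The 3001/3002 induction rule leaves Day 1 severity open. A subject who starts and stays at or below the cut-off counts as a remitter and, unless the score halves again, as a non-responder. No planned analysis separates these subjects from those who reach remission under treatment.

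The size is unknown. With the base assumptions in Step 3, remission rises by 5.0-6.5 points at a 10% share and by 10-13 points at 20%. Response falls by 0.5-3.0 and 1-6 points. The shares and the underlying rates are all assumptions. No error rate is affected, because the efficacy analyses are descriptive.

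A reader might also conclude that the planned denominator is wrong and should be replaced. That goes too far. Protocol 11.4 and SAP 5.2 plan these rates for the Full (IND) set, and SAP Amendment 2 is dated 14 February 2023, after the December 2022 limit on participation. A supplementary breakdown answers the question without changing the main analysis at that stage.

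**What to change.** Keep the Full (IND) tables in SAP 5.2.1.2 and 5.2.3.2 as planned. For the induction phase, and for the 3003-relapse subgroup, add:

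- (a) the number in remission at the induction baseline (MADRS ≤ 12; PHQ-9 < 5 for the PHQ-9 table), and the share still in remission at each visit and at End Point (IND);
- (b) response and remission among subjects not in remission at that baseline.

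Use (b) wherever the report describes remission achieved during induction. Define Baseline (IND) explicitly in SAP 2.2.

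Reconcile two sets of passages: the 6-month follow-up wording in protocol 3.2.1 and SAP 1.2 with the 2-week wording in protocol 4.1 and 9.1.2 and the induction list in SAP 1.2; and the non-response wording in protocol 3.2.2 with criterion 1.1 a.i.

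The cost is a few table lines from data already collected. The denominator for (b) is smaller and differs between the MADRS and PHQ-9 tables, and the remission rate in (b) may be lower than the one in the main table.
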